This is a prospective placebo-controlled randomized study. Patients will enter with active disease. After informed consent and screening procedures are completed, enrolled patients may be optionally treated with intramuscular methylprednisolone acetate and background immune-suppressive medications will be withdrawn. Injection of methylprednisolone acetate may be repeated in week 2 at the discretion of the investigator, to induce a state of remission/low disease activity. Patients will be assigned to begin the study medication upon enrollment (baseline, week 0). Patients will be randomized 1:1 to Aggrenox or half of an 81mg aspirin tablet twice daily for 24 weeks. Aggrenox will be initiated at a single bedtime dose for a week, followed by twice daily administration for the rest of the study, to minimize the risk of side effects (e.g. dizziness, headache). Aspirin will be titrated similarly to preserve blinding. Gelatin capsules will be used to cover the pills in order to preserve the blinding.

Participants will be evaluated at baseline (week 0), week 2, week 4 and every 4 weeks until the completion of the study at week 24. An additional study visit may be scheduled at the time of a clinically significant flare (flare visit). Evaluation of general health status, adverse events and lupus disease activity (SLEDAI, BILAG, PGA, CLASI, DIAL, SF-36v2, Lupus QoL, FACIT-fatigue, PSQI, CES-D) will be performed at baseline, week 4 and every subsequent visit. Time to first flare and severity of first flare will be examined. At the time of a clinically significant flare

(defined as at least one BILAG letter grade increase or an increase of ≥ 3 points in SLEDAI AND clinician determination of clinically significant deterioration) patients may elect further treatment with intramuscular methylprednisolone acetate or, if necessary DMARD therapy, but will continue the study as permanent nonresponders.

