Patients will have CBC with differential, metabolic profile, urinalysis, anti-dsDNA, and complement studies performed at baseline, each of the subsequent monthly visits through week 24 and the flare visit. If urine dipstick is $\geq 2+$, a protein/creatinine ratio will be performed at the following visit (or sooner at the discretion of the investigator). Pharmacodynamic and exploratory blood and urine biomarker samples will be drawn prior to first dose at baseline, at weeks 8 or 12, week 24 and at the flare visit. Some of the stimulated cell gene expression and signaling pathway work will be performed on deidentified samples in collaboration with Drs. [name] and [name] at Beth Israel Medical Center in Boston Massachusetts. We will have a material transfer agreement with that institution. In the context of our ancillary study of heart rate variability in lupus, a 5-minute ECG will be performed at each monthly visit and at the flare visit (please see attached protocol).

Summary of Medications and Medication Changes

At screening, participants may be receiving daily prednisone at a dose of 20mg or less, and/or one or more of the following DMARDs: hydroxychloroquine, methotrexate, azathioprine and mycophenolate mofetil, and must be agreeable to discontinue their background immune suppressants upon enrollment. Patients taking hydroxychloroquine upon enrollment will however continue the medication throughout the study.

All participants may be administered optional intramuscular methylprednisolone acetate upon enrollment (usually 160mg, but dose may adjusted based on clinical judgment). Intramuscular steroid treatment may be repeated at weeks 2 at the discretion of the investigator, to induce a state of remission/low disease activity while background medications are withdrawn. Patients on oral steroids will be given an optional rapid taper over 3-4 weeks.

Duration of participation

Participants will receive treatment for a total of 24 weeks.

Patient enrollment

A maximum of 50 patients meeting the inclusion criteria and not meeting the exclusion criteria will be enrolled in the study. The enrollment period is expected to last for at least 18 months but could last as long as four years.

Data collection and analysis

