Data will be collected by study personnel who will be kept blinded to treatment assignments. A trained study coordinator will provide data monitoring and quality assurance checks on the database. The final data will be pooled and analyzed by the investigators.

E. Statistical methods

The primary analysis will be an intention-to-treat two by two table.

Primary endpoint: A two by two table analysis of rate of response by the BICLA response index at week 24 compared to baseline (week 0) in patients on aspirin versus Aggrenox regimens, with non-response attributed to patients who receive defined non-responder treatments and/or withdraw early. Please see below for power calculations based on expected response rates. Independent predictors of BICLA response, including baseline biomarkers, biomarker responses to Aggrenox treatment, demographics and amount of steroids administered, will be further investigated by exploratory logistic regression modeling.

Secondary endpoints: Flare rates at week 24 compared between completers among treatment groups. Time to flare (log rank test). SRI 4/5 at week 24, BICLA and SRI 4/5 at each month. HRQOL comparing treatment groups versus baseline at week 24 and at each month. Although our primary endpoint is based on the BICLA response, an accepted outcome for lupus clinical trials which serves as a pilot response indicator for future trials, it is likely that some secondary endpoints, such as time to flare will be more sensitive, and more likely to achieve significance in a pilot study.

Exploratory endpoints: SRI component analyses and CLASI responses. Refinement in BICLA and SRI analysis using a propensity score derived by multiple potential confounders identified in exploratory single variate analysis. Relation of clinical and biologic endpoints with heart rate variability measures by multivariate analysis.

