Biologic Endpoints: Changes in B cell and T cell subsets, relevant gene expression patterns, B-T cytokine profiles and cell-bound complement split products and urinary biomarkers at baseline versus week 24 in each treatment group. Evaluation of B Cell/T cell expression patterns in patients with higher versus lower IL6, IL17 and IL23 expression detected at baseline. These endpoints will be evaluated both as changes with Aggrenox versus aspirin treatment (non parametric analysis) and as components of multivariate modeling and propensity score analysis as described above. An exploratory responder analysis will also be performed (changes in these biomarkers with response versus non-response in patients receiving Aggrenox). The latter analysis may need to be observational only, as it is likely to be underpowered and diluted by patients who may not have begun the trial with the characteristic abnormalities in T cell subset activity.

Power/Sample size calculation

We base this calculation on preliminary data from the BOLD study (11) which is an exploration of underlying biology in patients with SLE who receive steroids and are withdrawn from background treatments, in other words identical to the aspirin group in the current proposal. To date we have analyzed data from 31 patients who completed the BOLD protocol and these outcomes suggest that no more than 20% of the aspirin group will achieve a BICLA response at week 16 (range 1-20%) and no more than 5% achieves a BICLA response at week 24 (range 0-10%). Assuming a 35 to 50% response rate in the Aggrenox group at week 24, a sample size of 50 patients will provide a power around 80% at a significance level of 0.05 at week 24. By these settings and assumptions, the following power estimates are obtained.

Power calculations for a 50 patient study, if alpha=0.05 with response rates:

	Rate 1	Rate 2	Rate 3	Rate 4	Rate 5	Rate 6	Rate 7
Aggrenox n=25	60%	55%	50%	45%	40%	35%	35%
Aspirin n=25	20%	15%	10%	10%	5%	5%	3%
power	0.84	0.86	0.89	0.80	0.86	0.77	0.84

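### The exploratory propensity score for BICLA and SRI takes its variables from a single-variable screen of the trial data, which attenuates the effect or adds variance; a short fixed baseline list avoids both

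*Combined protocol and SAP*

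**What the plan says.** Section E fixes the primary analysis first: "The primary analysis will be an intention-to-treat two by two table". Under exploratory endpoints it then adds "Refinement in BICLA and SRI analysis using a propensity score derived by multiple potential confounders identified in exploratory single variate analysis". Section D sets the design: "Patients will be randomized 1:1 to Aggrenox or half of an 81mg aspirin tablet twice daily for 24 weeks". The enrolment paragraph caps the trial: "A maximum of 50 patients meeting the inclusion criteria and not meeting the exclusion criteria will be enrolled in the study".

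The exploratory sentence states how variables get into the score: by single-variable analysis of this trial's data. It does not say whether the screen is against arm or response, at what cut-off, from which candidates, or whether the score becomes a covariate, a weight or a matching variable. The Biologic Endpoints paragraph of section E also sends biomarker changes between baseline and week 24 into the propensity score analysis.

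**The concern.** A propensity score is meant to remove systematic differences in who gets which treatment. Randomisation has already done that in expectation, so a screen of pre-dose variables can pick up only chance. What it does depends on its target.

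- **Screen against arm.** The score collects the variables most collinear with treatment, whether or not they predict response. The estimate stays unbiased, but its variance rises.
- **Screen against response.** When the drug works, response and arm are correlated. A variable that matches response by chance therefore tends to lean towards the same arm, and adjusting for it removes part of the real effect.

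At stake is the reading of an analysis presented as a refinement. An adjusted difference that is smaller or less precise could be taken as evidence of confounding in the 2x2 result. The size of the estimate matters in this pilot, because the text after the power table says that an absolute difference of 12% or more might justify a larger study without statistical significance.

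**Working it through.** **1. Inputs from the plan.** Section E gives 25 per arm and alpha 0.05, with "Assuming a 35 to 50% response rate in the Aggrenox group at week 24" and at most 5% on aspirin. The claim is that "a sample size of 50 patients will provide a power around 80% at a significance level of 0.05 at week 24". The table's entry for 35% v 5% is 0.77.

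**2. Reproducing the plan's figure.** Two-sided normal approximation with pooled variance, no continuity correction, pooled rate (0.35 + 0.05)/2 = 0.20:

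- null SE = √(2 × 0.20 × 0.80 / 25) = 0.1131
- alternative SE = √((0.35 × 0.65 + 0.05 × 0.95) / 25) = 0.1049
- z = (0.30 − 1.96 × 0.1131) / 0.1049 = 0.75, so power = 0.77

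All seven table entries reproduce this way to within 2 points, so a Pearson-type test is a fair comparator. Computed exactly rather than by approximation, power at 35% v 5% is 0.826 for uncorrected Pearson and 0.704 for two-sided Fisher.

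**3. Why a response screen attenuates.** The correlation between arm and response at these rates is 0.30 × 0.5 / √(0.20 × 0.80) = 0.375. A pure-noise variable with chance correlation r with response therefore has expected correlation 0.375r with arm, in the same direction. With 20 noise candidates and a cut-off of p < 0.10, 20 × 0.10 = 2 such variables enter on average.

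**4. Simulation at 35% v 5%.** 25 per arm, pre-dose candidates unrelated to response, logistic score for arm, score entered as a linear covariate. Assumed: 5 to 40 candidates, cut-offs 0.05 to 0.20. Unadjusted: mean difference 0.30, Pearson power about 0.83.

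| Candidates | Screen | Mean difference | Power |
|---|---|---|---|
| 5 | either | – | loss about 1-5 points |
| 10 | either | – | loss about 3-9 points |
| 20 | arm | unbiased | 0.70-0.77 |
| 20 | response | 0.26-0.28 | 0.66-0.76 |
| 20-40 | arm | unbiased | 0.59-0.77 |
| 20-40 | response | 0.23-0.28 | 0.50-0.76 |

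At 20 candidates the loss is 0.83 − 0.77 = 6 points to 0.83 − 0.66 = 17 points. For 10 to 20 candidates together, about 5-17 points is a fair summary; the 3-point loss is the mildest result with 10.

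**5. Other rates.** At 45% v 10% with 20 noise candidates and p < 0.10:

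- response screen: difference 0.350 to 0.314, power 0.839 to 0.737-0.755
- arm screen: SD 0.118 to 0.129-0.135, power 0.836 to 0.749-0.784

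The loss is not only an effect of the linear model. With a logistic likelihood-ratio test in the same setting, power went from 0.835 to 0.766 (response screen) and from 0.851 to 0.785 (arm screen).

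**6. Type I error.** With 20% in both arms it was 0.037-0.067 for the screened score and 0.049-0.060 for the table. There is no clear false-positive cost.

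**7. A fixed list instead.** With three to five truly prognostic baseline variables and no screen, the difference stayed at about 0.35, its SD fell from 0.106-0.119 to 0.099-0.109, and power was about equal to or above the table's. With four non-prognostic variables at 35% v 5%, power was 0.82 (likelihood ratio) or 0.77 (linear model), against 0.82 unadjusted.

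**8. Post-baseline variables.** If the score includes markers that the drug moves and that drive response (assumed shift 0.8 SD, log odds ratio 0.6 each), a true difference of 0.35 falls to 0.20-0.25 and power to 0.33-0.61, whichever screen is used.

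**The case against.** A reader might infer that the refined result must be weaker than the 2x2 table. The documents do not support that, for two reasons.

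- **Candidates.** The plan gives no list. With 3 to 5 strongly prognostic candidates, the screened score matched or beat the table in several settings (best case 0.853 unadjusted, 0.873-0.900 adjusted). A long list is plausible, given the disease activity indices, questionnaires, laboratory tests and biomarker families collected, but it is an inference.
- **Comparator.** Section E names no test for the table. Against Fisher (0.704), inverse weighting after an arm screen (0.72-0.79 with 20 or 40 candidates) is above the table, and the covariate-adjusted results lie on both sides of it.

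Both objections stand and limit the power claim. Neither removes the attenuation under a response screen, which also appeared with short prognostic lists (0.327-0.343 against a true 0.35).

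It is also fair to say that the analysis is labelled exploratory, that no decision rule uses it, and that on average the attenuated difference at the planning rates stays well above 12%. That limits the consequence. It does not justify the screen, since a better rule costs almost nothing.

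**Conclusion.** The concern holds in limited form. Choosing propensity variables by a single-variable screen of a randomised trial of at most 50 patients is worse than a fixed baseline list. Screening on response attenuates a real effect (0.30 to about 0.26-0.29 with 10 to 20 uninformative candidates at 35% v 5%). Screening on arm adds variance without bias. The power loss against Pearson is about 1-5 points with 5 candidates and about 5-17 with 10 to 20. These sizes rest on assumed candidate numbers and cut-offs and on mostly uninformative candidates; with a few strong predictors the power loss can vanish.

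Two further inferences go too far. The primary result is not compromised, because the intention-to-treat table does not use the score. Nor do the documents show that adjustment would raise power: nothing in them establishes which baseline variables predict week-24 BICLA.

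The January 2015 amendment temporarily interrupts the randomised part. If fewer than 50 patients are analysed, the problem would be worse.

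**What to change.** In the exploratory endpoints paragraph, delete the clause that draws the confounders from a single-variable screen. Before unblinding, fix three or four week-0 variables expected to be prognostic, for example SLEDAI score, any BILAG A, hydroxychloroquine use and prednisone dose. State that only baseline values enter, so that the week-24 biomarker changes in the Biologic Endpoints paragraph stay out of this adjustment. Name the adjustment method; penalised logistic regression with standardisation is one option. Report the covariate-adjusted BICLA and SRI risk differences beside the 2x2 table.

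The cost is a sentence or two of wording, with no new data collection. The gain is freedom from selection-induced attenuation and variance; power improves on the unadjusted table only if the listed variables are in fact prognostic. The downside is that a chance imbalance in an unlisted variable is described but not adjusted for.

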Only certain SLE subgroups or organ systems may respond to a particular agent, an important consideration for early phase trials. Concurrent use of immunosuppressive medications, like mycophenolate mofetil, azathioprine, methotrexate and corticosteroids, creates further biologic variability in an already heterogenous disease and confounds the interpretation of data in human studies, since these medications might interfere with or confound the mechanism of the agent(s) studied. This practice also increases the response in the comparator arms, limiting the possible differences between treatment and placebo in SLE clinical trials, necessitating the prolonged study of larger patient numbers for adequate power, and further compromising the clinical interpretability of results. Withdrawal of background immune suppression has been considered as an option to limit study time and patient exposures to untested therapies, but the community has been concerned about its safety. The BOLD (Biomarkers of Lupus Disease) trial, in which a brief course of parenteral steroids is utilized to induce a state of remission or low disease activity while background medications are withdrawn, has shown evidence this approach is safe and effective (11). Time to first flare averaged 72 days (CI 43–91), with 100% of the patients flaring by 24 weeks.

In the BLISS trials of belimumab in SLE the systemic response index (SRI), a composite measure of disease activity, was used as the primary endpoint. SRI is a landmark index defined as the composite of ≥ 4 point reduction in total SLEDAI score, with no new BILAG A or no more than one new BILAG B domain score and no more than 10% worsening in physician's global assessment (PGA), compared to baseline. Another composite measure, the SRI-BILAG (BICLA) has been used in the EMBLEM phase II trial of epratuzumab in SLE. BICLA requires the achievement of BILAG-2004 improvement (BILAG A to B/C/D, BILAG B to C/D, and no BILAG worsening), along with no deterioration in SLEDAI total score and no more than 10% worsening in PGA. In the BOLD study, BICLA was found to be more sensitive to change than SRI, when anchored to the simpler BOLD improvement criteria (drop of \geq one BILAG grade or ≥ 4 SLEDAI points) anchored to the clinician's determination of significant clinical improvement (11).

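### Between-arm biomarker change is analysed only at week 24, where it includes treatment after flare, and no analysis names the scheduled week 8 or 12 samples

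*Combined protocol and SAP*

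**What the plan says.** - **Analysis time.** Section E, Biologic Endpoints, takes cell subsets, gene expression, cytokines and "cell-bound complement split products and urinary biomarkers at baseline versus week 24 in each treatment group". It then evaluates these endpoints as "changes with Aggrenox versus aspirin treatment (non parametric analysis" and as components of multivariate and propensity models. The non-parametric test is not named, nor is any adjustment for the baseline value.
- **Sampling.** Section D schedules biomarker samples before the first dose, at week 8 or 12, at week 24 and at the flare visit.
- **Other repeated analyses.** BICLA, SRI and quality of life are analysed monthly (for the last, "HRQOL comparing treatment groups versus baseline at week 24 and at each month"). Biomarkers are not in that list.
- **Treatment after flare.** Section D: "patients may elect further treatment with intramuscular methylprednisolone acetate or, if necessary DMARD therapy, but will continue the study as permanent nonresponders".
- **Handling of that treatment.** The primary endpoint counts responders "with non-response attributed to patients who receive defined non-responder treatments and/or withdraw early". This is a rule for BICLA. No corresponding rule exists for biomarker values.
- **Expected flares.** Section C reports for the earlier withdrawal study: "Time to first flare averaged 72 days (CI 43–91), with 100% of the patients flaring by 24 weeks". The power section calls that study's setting "in other words identical to the aspirin group in the current proposal".
- **Amendment of January 13, 2015.** The randomised part is temporarily interrupted to concentrate on the drug's pharmacology. Group B receives open-label Aggrenox for 3 months without a control arm. Additional steroids are barred, but treatment is permitted after flare or with persistently active disease.

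**The concern.** Section C justifies withdrawing background drugs because they may confound the mechanism under study. Treatment after flare can bring the same classes of drug back before the only time point at which biomarkers are compared between arms. If Aggrenox prevents flares, more aspirin patients will probably have been treated by week 24. A small difference could then mean that the drug does little to the marker, or that rescue moved the aspirin arm the same way. A large one could include rescue acting in the opposite direction.

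The power section says that the biomarker work might be used to refine entry criteria and biologic treatment goals for a further study. Entry criteria can rest on baseline markers, which rescue cannot change. Treatment goals are better served by knowing what the drug itself does to a marker. The earlier samples could help with that, but no analysis is assigned to them.

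**Working it through.** **1. Is there a figure to reproduce?** The plan gives no effect size or power for any biomarker. Its BICLA power table does reproduce: the pooled-variance normal approximation, two-sided 0.05, 25 per arm, gives 0.845, 0.866, 0.895, 0.811, 0.865, 0.772 and 0.844 against the stated 0.84, 0.86, 0.89, 0.80, 0.86, 0.77 and 0.84. The planned rates are used below only to judge how unequal rescue might be.

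**2. How unequal could rescue be at week 24?** Planned BICLA response is 5% on aspirin and 35 to 50% on Aggrenox, so non-response is 95% against 65 to 50%, a gap of 30 to 45 points. Rescued patients are a subset of non-responders. If half of the non-responders in each arm take treatment (assumption), the gap in patients rescued is 0.5 × 30 = 15 to 0.5 × 45 = 22.5 points. If the drug has no effect on flares, the gap is about zero.

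**3. Effect on the week-24 difference.** Assumptions: gap in patients flared G = 25 to 50 points (this spans the 30 to 45 above), uptake u = 50 to 80% in both arms, rescue effect e = 0.3 to 0.6 SD, simple addition of effects, unchanged variance.

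Shift = G × u × e
- low: 0.25 × 0.5 × 0.3 = 0.0375 SD
- high: 0.50 × 0.8 × 0.6 = 0.24 SD

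For a true 0.8 SD (noncentral t as an approximation, 25 per arm, two-sided 0.05):

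| Direction of rescue | Observed difference (SD) | Power |
|---|---|---|
| none | 0.80 | 0.79 |
| same as the drug | 0.76 to 0.56 | 0.75 to 0.49 |
| opposite to the drug | 0.84 to 1.04 | 0.83 to 0.95 |

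**4. Is week 8 or 12 cleaner?** Section C gives only an average of 72 days, a CI of 43 to 91 and 100% by 24 weeks. It gives no distribution and does not say whether the average is a mean or a median. Every share below is therefore modelled. The exponential is F(t) = 1 − 2^(−t/median) or 1 − exp(−t/mean). The beta curve runs over 0 to 168 days with the mean and SD shown (SDs assumed).

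| Assumed curve, aspirin arm | Flared by week 8 | By week 12 | By week 24 |
|---|---|---|---|
| Exponential, median 72 | 42% | 56% | 80% |
| Exponential, median 43 to 91 | 60 to 35% | 74 to 47% | 93 to 72% |
| Exponential, mean 72 | 54% | 69% | 90% |
| Beta, mean 72, SD 28 to 48 | 31 to 43% | 66 to 60% | 100% by construction |
| Beta, mean 91, SD 20 | 4% | 36% | 100% by construction |

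Under every curve there are fewer post-flare values at week 8 or 12 than at week 24, but never none.

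**5. Baseline adjustment, a separate matter.** The comparator is a Wilcoxon test on change, which is one reading of the plan's unnamed method. The alternative regresses the rank of the follow-up value on the rank of baseline and arm. Simulation: normal data, 25 per arm, 10,000 runs, Monte Carlo SE at most 0.005.

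| Baseline correlation | Power at 0.8 SD, change | Power at 0.8 SD, rank ANCOVA |
|---|---|---|
| 0.3 | 0.62 | 0.80 |
| 0.5 | 0.76 | 0.86 |
| 0.7 | 0.93 | 0.95 |
| 0.85 | 1.00 | 1.00 |

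Type I error is 0.04 to 0.06 for both. In the largest rescue case of step 3, at correlation 0.5, power is 0.43 against 0.53. Adjustment helps there too, but the difference being tested still includes rescue.

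**The case against.** **The week-24 comparison is sound as it stands.** This is correct for the effect of assignment. A reader might infer that rescue invalidates the test. It does not: with no drug effect, rescue does not differ systematically by arm and the test keeps its level. What is lost is the reading as a direct drug effect.

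**The plan already has tools for this.** The exploratory model of BICLA response includes "biomarker responses to Aggrenox treatment, demographics and amount of steroids administered, will be further investigated by exploratory logistic regression modeling". The biomarker responses there carry no date and could use the week 8 or 12 values. But steroid amount enters as a predictor of BICLA, not as a rule for biomarkers, and adjusting for treatment taken after randomisation would not simply recover the direct effect. The responder analysis within Aggrenox does not settle it either. Its responders cannot have had defined non-responder treatment, but its non-responders may have.

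**Group B addresses the pharmacology.** The amendment gives that question its own phase and bars additional steroids. This weakens the concern. It does not remove it, because group B has no control arm and permits treatment after flare. A reader might infer that week 8 or 12 is the only biomarker time point shared by the two groups. The amendment gives group B no sampling schedule of its own, and flare-visit samples could also be shared.

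**Week 8 or 12 is not clean.** This stands. Flares will already have occurred, and the enrolment and week-2 steroid may still be acting. The week-2 injection is discretionary and comes after study drug starts, so it could differ by arm. A reader might also infer an ordering of the between-arm gap across visits. The documents do not support one. With an assumed hazard ratio of 0.5, the gap exp(−λt/2) − exp(−λt) is 18, 22 and 25 points at weeks 8, 12 and 24 for an exponential with median 72 days (λ = ln 2/72), but 22, 25 and 21 points with mean 72 days (λ = 1/72). A curve fixed at 100% on day 168 forces the gap to zero there. The order follows from the chosen curve.

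**Conclusion.** The point holds in a limited form. Week 24 is the only time named for the between-arm biomarker comparison. No rule covers values after rescue, and no analysis names the week 8 or 12 samples. The week-24 difference is a valid effect of assignment including rescue. It is a direct drug effect only if rescue does not differ by arm or does not move the marker.

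Unequal rescue is an inference from the planned response rates, not a stated fact. The shift of 0.04 to 0.24 SD rests on assumed gap, uptake and effect, and its sign may differ by marker. The background section reports that dipyridamole amplifies steroid effects, so even simple addition may fail. The flare shares should not be read as figures from the earlier study. BICLA is unaffected, and these are exploratory endpoints in a pilot. Worth considering, at modest priority.

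**What to change.** Before unblinding, amend the Biologic Endpoints paragraph for group A:

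1. Add a prespecified between-arm analysis of the week 8 or 12 samples already scheduled. Record which week each sample comes from, and flag values taken after rescue or after the enrolment or week-2 steroid.
2. Specify the between-arm biomarker comparison as a rank ANCOVA adjusted for the baseline value. This is for precision; it does not separate the drug from rescue.
3. Keep the all-patients week-24 comparison, label it as regardless of rescue, and report the percentage rescued by arm beside it.

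Items 1 and 2 are the substance; item 3 alone would change little. The cost is SAP wording, dates for rescue and the early steroid injections, and a little more analysis. No sample, visit or treatment rule changes. The downsides are further exploratory comparisons and an earlier time point with fewer post-flare values but not free of them.
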